#### **4.3.2. Primary Analysis Relative to the Efficacy Estimand**

The primary analysis relative to the “efficacy” estimand will be conducted using HbA1c data in the EAS from baseline through the 40-week visit with the aid of MMRM. Restricted maximum likelihood (REML) will be used to obtain model parameter estimates, and the Kenward-Roger option will be used to estimate denominator degrees of freedom. The response variable of the MMRM model will be change in HbA1c values from baseline obtained at each scheduled postbaseline visit. The independent variables of the MMRM model are treatment, visit, treatment-by-visit interaction, number of background OAMs (0 to 1, 2 to 3), dulaglutide dose at screening, and region as fixed effects, and baseline HbA1c as covariate. Missing data will be addressed by the MMRM model. No explicit imputation methods for missing data will be employed.

An unstructured covariance matrix will be used to model the within-patient errors. If this model fails to converge, the following covariance structures will be tested in the following order:

1. Heterogeneous Toeplitz
2. Heterogeneous First Order Autoregressive
3. Heterogeneous Compound Symmetry
4. Toeplitz
5. First Order Autoregressive
6. Compound Symmetry

The first covariance structure that converges will be used. The resulting least squares mean estimate of mean change from baseline in HbA1c will be summarized by visit and by study treatment.

With the aid of the MMRM analysis, p-values and 2-sided 95% CIs for mean change in HbA1c from baseline to the 40-week visit will be derived and summarized for the tirzepatide 15 mg or MTD arm compared to dulaglutide 4.5 mg or MTD arm

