9.3.2. Primary Endpoint Analysis

The primary endpoint for this study is change from baseline in HbA1c to the 40-week visit (Visit 11). This endpoint will be used to evaluate the primary objective of the study for both the treatment-regimen and the efficacy estimands (Section 3). The null hypothesis corresponding to the primary objective is specified in Section 9.1.

The primary objective based on the treatment-regimen estimand defined in Section 3 will be evaluated based on the FAS dataset (Section 9.2) using an ANCOVA for change from baseline in HbA1c at Week 40 with terms for

- treatment (tirzepatide, dulaglutide)
- number of background OAMs (0-1 or 2-3)
- dulaglutide dose at screening (0.75 mg or 1.5 mg)
- region (NA, EU), and
- baseline value.

For the purpose of the treatment-regimen estimand, missing HbA1c values at the 40-week visit will be imputed based on observed data in the same treatment group from participants who had their efficacy assessed after ED of study intervention. This analysis will be conducted with multiple imputations, and statistical inference over multiple imputations will be guided by the method proposed by Rubin (1987).

The primary objective based on the efficacy estimand defined in Section 3 will be evaluated using the EAS dataset (Section 9.2). The primary analysis model for HbA1c measurements over time will be an MMRM. The response variable of MMRM will be change in HbA1c values from baseline obtained at each scheduled postbaseline visit. The independent variables of the MMRM model are treatment, visit, treatment-by-visit interaction, number of background OAMs, dulaglutide dose at screening, region as fixed effects, and baseline HbA1c as covariate. Missing data will be addressed by the MMRM model. No explicit imputation methods for missing data will be employed.

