#### **4.4.1.1. Mean Changes in Body Weight (kg and lb) from Baseline at 40-week Visit**

The analysis for change in body weight (kg and lb) from baseline (postbaseline to baseline) at Week 40 will be conducted in a manner similar to the primary analysis in Section 4.3.1 (treatment-regimen estimand) and Section 4.3.2 (efficacy estimand) with the following differences:

- For the treatment regimen estimand, the ANCOVA model (Section 4.3.1), baseline category for HbA1c ( $\leq 8.5\%$ ,  $> 8.5\%$ ) will be used as a fixed factor in place of baseline HbA1c as a covariate, and baseline weight will be used as an additional covariate in the statistical model. Imputation of missing values at Week 40 will be done in a similar manner as described in Section 4.3.1. If value of the imputed weight change from baseline is  $<-50$  kg or  $>50$  kg, that value will be set to -50 kg or 50 kg, respectively, to avoid unrealistic imputed values. Similar imputed values (equivalent to kg) will be used for body weight change (lb) from baseline endpoints, to avoid unrealistic imputed values.
- For the efficacy estimand, the MMRM model (Section 4.3.2) will be updated by adding the baseline category for HbA1c ( $\leq 8.5\%$ ,  $> 8.5\%$ ) as a fixed factor in place of baseline HbA1c and baseline weight as an additional covariate. Missing data will be addressed by the MMRM model, and no explicit imputation methods will be used.

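### The efficacy-estimand MMRM fits one baseline HbA1c slope for Weeks 4 to 40; a baseline-by-visit term would probably sharpen the Week 40 estimate slightly, at almost no cost

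*SAP*

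**What the plan says.** SAP Section 4.3.2 models "change in HbA1c values from baseline obtained at each scheduled postbaseline visit". It lists the model terms as follows: "The independent variables of the MMRM model are treatment, visit, treatment-by-visit interaction, number of background OAMs", then "dulaglutide dose at screening, and region as fixed effects, and baseline HbA1c as covariate". Protocol Section 9.3.2 gives the same list: "number of background OAMs, dulaglutide dose at screening, region as fixed effects, and baseline HbA1c as covariate". Only treatment is crossed with visit, so baseline HbA1c has a single coefficient for Weeks 4, 8, 12, 16, 20, 24, 32 and 40. On the error structure, "An unstructured covariance matrix will be used to model the within-patient errors", and "the Kenward-Roger option will be used to estimate denominator degrees of freedom".

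The weight MMRM in SAP Section 4.4.1.1 is built from the same model, with the HbA1c category entered "as a fixed factor in place of baseline HbA1c and baseline weight as an additional covariate". Neither document has a baseline-by-visit term, even as a sensitivity analysis. The treatment-regimen ANCOVA (SAP Section 4.3.1) uses only Week 40 data, so it fits its own Week 40 slope and is not affected.

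**The concern.** A single slope is efficient at Week 40 only if baseline relates to change in the same way at every visit. The dosing schedule makes that unlikely. Under Protocol Section 6.1.1, tirzepatide starts at 2.5 mg and rises by 2.5 mg every 4 weeks, so 15 mg cannot be reached before Week 20. Dulaglutide also rises in 4-week steps. HbA1c reflects glycaemia over a long period, so little of the response, and little of its dependence on baseline, can show at Week 4.

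If the slope steepens, the pooled coefficient is pulled towards the early visits and adjusts Week 40 too weakly. No other term makes up for this: Protocol Section 9.3.1 leaves the HbA1c category out of HbA1c models, so the continuous slope carries all the baseline adjustment. At stake are some precision in one of the two primary analyses and incomplete correction of any chance baseline imbalance.

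**Working it through.** **1. The plan's own figures (SAP Section 5).** Treatment-regimen estimand, difference 0.58, SD 1.3: n per arm = 2 × (1.960 + 1.282)² × 1.3² / 0.58² = 105.6, so 106. Dividing by 0.85 for 15% discontinuation gives 125 per arm, or 250. Efficacy estimand, difference 0.60, SD 1.1, t-test: power is 97.7% at 106 per arm and 99.0% at 125. The stated figure of at least 95% is reproduced, with no credit taken for baseline adjustment.

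**2. Assumed inputs.** The documents give no baseline SD, slopes by visit or between-visit correlation. Eligibility runs from 7.0% to 9.5% at screening; a uniform spread would have SD 2.5/√12 = 0.72, so 0.6 to 0.7 is a reasonable assumption. The central case takes baseline SD 0.65, a Week 40 slope of -0.5, and a Week 4 slope of 25% or 50% of that. Total Week 40 SD is held at the stated 1.1.

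**3. Formulas.** Let b be the vector of visit slopes, S the residual covariance and 1 a vector of ones. Under an unstructured covariance the single slope converges to c = (1'S⁻¹b) / (1'S⁻¹1). The Week 40 standard-error ratio, common slope over visit-specific slopes, is √[1 + Var(X)(b40 - c)² / s40²], where X is baseline HbA1c and s40² = 1.1² - 0.5² × 0.65² = 1.104, so s40 = 1.051.

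**4. Central case, with correlated visits and less residual spread early on.**

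| Week 4 slope | Correlation | c | Gap from -0.5 | SE ratio |
|---|---|---|---|---|
| -0.125 | AR(1) 0.9 | -0.106 | 0.394 | 1.029 |
| -0.125 | AR(1) 0.8 | -0.180 | 0.320 | 1.019 |
| -0.125 | exchangeable 0.6 | -0.061 | 0.439 | 1.036 |
| -0.25 | AR(1) 0.9 | -0.237 | 0.263 | 1.013 |
| -0.25 | AR(1) 0.8 | -0.287 | 0.213 | 1.009 |
| -0.25 | exchangeable 0.6 | -0.207 | 0.293 | 1.016 |
| -0.5 (equal) | any | -0.500 | 0 | 1.000 |

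First row: √(1 + 0.4225 × 0.394² / 1.104) = √1.059 = 1.029.

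**5. Without the early-variance assumption.** If residual SD is constant and correlation exchangeable, c is the plain mean of the visit slopes. The mean visit week is 156/8 = 19.5. With slopes linear in time from -0.125 to -0.5, c = -0.125 - 0.375 × 15.5/36 = -0.286. The ratio is √(1 + 0.4225 × 0.214² / 1.104) = 1.009. The loss shrinks but does not vanish.

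**6. Range.** A simulation with 250 participants, eight visits and an estimated unstructured covariance (1,500 runs) gave Week 40 variance ratios of 1.014 (slopes -0.1 to -0.4, SD 0.6) and 1.061 (slopes -0.2 to -0.6, SD 0.7). In standard error these are √1.014 = 1.007 and √1.061 = 1.030. Closed-form values for slopes of this kind reach about 11% in variance, √1.11 = 1.054. Hence about 1% to 5%.

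**7. Validity.** A second simulation (600 trials per scenario, 15% dropout missing at random) used a true difference of -0.60. Mean estimates ran from -0.596 to -0.609 and coverage from 0.94 to 0.96 under both models; the simulation error of a 95% coverage figure is √(0.95 × 0.05/600) = 0.9 points. With a Week 40 slope of -0.5 and a Week 4 slope of -0.125, the fitted common slope averaged -0.11 and the model-based SE ratio was 1.026. With equal slopes the ratio was 0.9975, so the unneeded term cost about 0.25%. This simulation used normal critical values in place of Kenward-Roger and omitted the OAM, dose and region terms.

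**8. Power at 106 per arm.** In the central case it is 97.9% to 98.4% with the common slope and 98.5% with visit-specific slopes.

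**The case against.** The strongest objection is that the slopes are assumed. Nothing in the documents shows that they differ, and if they are equal the extra term gains nothing. That stands: the dosing schedule supports the direction but not the size.

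A reader might infer more than the documents support:

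- **That the analysis is biased or the trial at risk.** Both models were unbiased on average with nominal coverage, and power is about 98% against a stated 95%. Even at the extreme of the values tried (baseline SD 0.8, Week 40 slope -0.7, SE ratio 1.13) the gain is about 1.3 points, and SD 0.8 is wider than a uniform spread over the eligibility range.
- **That chance imbalance is a serious threat.** Randomisation is stratified by HbA1c at 8.5% in blocks of 2 (Protocol Section 6.3). Under assumed HbA1c distributions, this cuts the chance of a baseline imbalance above 0.1% from 18-30% to 4-12%. With the central gaps, such an imbalance leaves 0.1 × 0.21 to 0.44, or 0.02 to 0.04 percentage points, uncorrected against an assumed effect of 0.60.
- **That participants could be saved.** The 250 is set by the treatment-regimen estimand, whose ANCOVA is unaffected.
- **That the MMRM and ANCOVA must adjust alike.** They serve different estimands with different data sets and missing-data methods; nothing requires a common slope.

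It is also fair to say that changing a prespecified primary model in an open-label trial carries a credibility risk. That bears on timing, and the fix allows for it.

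**Conclusion.** This is a cheap improvement to precision, not an error. The model does impose one baseline slope; that is certain from the text. That it under-adjusts at Week 40 is likely, because both arms are still escalating at the early visits, but it is not shown. The 1% to 5% is indicative, not a bound: it rests on the assumed slopes, baseline SD, correlation and growth of residual spread over time. The comparison is lopsided, with about 0.25% of standard error at risk if the slopes are equal. No estimand, endpoint, hypothesis or conclusion about power changes. The same reasoning applies to weight, where no slopes or SD were available and nothing has been quantified.

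**What to change.** Add baseline HbA1c-by-visit to the MMRM in SAP Section 4.3.2, and baseline weight-by-visit to the weight MMRM in SAP Section 4.4.1.1. Record the change and its reason in SAP Section 4.9, which now lists only the exclusion of data after non-study tirzepatide or dulaglutide. Because the trial is open-label, specify it before any outcome data are reviewed by arm; database lock is too late a deadline.

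The cost is seven more parameters per model (eight slopes in place of one) with about 250 participants, and a documented departure from Protocol Section 9.3.2. Protocol Section 9.3.1 and SAP Section 4.1 allow this through the SAP unless it counts as a principal feature of the protocol. No new data are needed. SAP Section 4.4.2.2 imputes missing values for the binary outcomes from the Section 4.3.2 MMRM, so it should say that those predictions use the revised model.

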## 4. Statistical Analyses

### 4.1. General Considerations

Statistical analysis of this study will be the responsibility of Lilly or its designee. The statistical analyses will be performed using SAS® Version 9.4 or higher.

Any change to the data analysis methods described in the protocol will require an amendment ONLY if it changes a principal feature of the protocol. Any other change to the data analysis methods described in the protocol, and the justification for making the change, will be described in the SAP or clinical study report (CSR). Some analyses and summaries described in this analysis plan may not be conducted if not warranted by data (for example, too few events to justify conducting an analysis). Listings of events will be provided in such situations. Additional exploratory analyses of the data will be conducted as deemed appropriate without further changes made to the protocol or SAP, even after final database lock.

All tests of treatment effects will be conducted at a 2-sided alpha level of 0.05/1-sided alpha level of 0.025, unless otherwise stated, and all confidence intervals (CIs) will be given at a 2-sided (95%) level. In statistical summaries and analyses, all data will be analyzed by randomly assigned treatment assignment. Participants will be analyzed according to the treatment they were randomly assigned to, regardless of the treatment actually received.

Baseline is defined as the last nonmissing measurement recorded on or before the randomization visit, prior to first dose of treatment, unless otherwise specified. For laboratory values, baseline needs to be prior the first dose time.

Efficacy analyses will use the Efficacy Analysis Set (EAS) to evaluate the efficacy estimand and the Full Analysis Set (FAS) to evaluate the treatment-regimen estimand. Safety will be assessed using Safety Analysis Set (SS). Selected safety analyses may be conducted after excluding data on rescue therapy or data after starting another antihyperglycemic medication.

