#### 4.6. Safety Analyses

Safety assessments will be done using the SS (See Section 3) irrespective of adherence to study intervention or initiation of rescue antihyperglycemic medication or prohibited medication, unless indicated otherwise. AEs will be coded from the actual term using the Medical Dictionary for Regulatory Activities (MedDRA) and reported with Preferred Terms (PTs) and System Organ Class (SOC). Selected notable AEs of interest may be reported using High-Level Terms (HLTs) or Standardized MedDRA Queries (SMQs). Summary statistics will be provided for incidence of treatment-emergent AEs (TEAEs), serious AEs (SAEs), and study discontinuation due to AEs, study intervention discontinuation due to AEs, or deaths from the time of first dose through the end of safety follow-up. Counts and proportions of participants experiencing AEs will be reported for each treatment group, and Fisher’s exact test will be used to compare the treatment groups.

Where necessary, for selected continuous safety parameters, the mean change from baseline at Week 40 will be assessed via MMRM using REML. Data from scheduled visits will be utilized for this analysis unless specified otherwise. The model for the analysis during the 40-week treatment period will include treatment, visit, treatment-by-visit interaction, number of background OAMs (0 to 1, 2 to 3), dulaglutide dose at screening, and region as fixed effects, and baseline value of the safety parameter as a covariate. To model the covariance structure within participants, the unstructured covariance matrix will be used. If this model fails to converge, the covariance structures specified in Section [4.3.2](#) will be tested in order until met convergence. If the data does not warrant the MMRM model, then ANCOVA model will be conducted. Where

necessary, the rate of events will be analyzed using a generalized linear MMRM assuming the number of events follow a negative binomial distribution and with treatment as a fixed effect.

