## 5. Sample Size Determination

Approximately 250 participants will be randomly assigned in a 1:1 ratio to each study arm. This sample size provides at least 90% power to detect a difference between treatment arms at Week 40 irrespective of adherence to treatment, changes in background OAMs or introduction of rescue antihyperglycemic medication. This sample size is based on an assumed treatment difference of 0.58% with a common standard deviation of 1.3%, using a 2-group t-test and a 0.05 two-sided significance level. The treatment difference is based on the following assumptions for the dose distribution for maximum dose or MTD:

- Tirzepatide MTD will be comprised of the following doses:
  - 15 mg dose - 80% of the participants
  - 10 mg dose - 15% of the participants
  - 5 mg dose - 5% of the participants
- Dulaglutide MTD will be comprised of the following doses:
  - 4.5 mg dose - 80% of the participants
  - 3.0 mg dose - 15% of the participants
  - 1.5 mg dose - 5% of the participants

In addition, the planned sample size provides at least 95% power to detect a difference between treatment arms at Week 40 after randomization regardless of changes in background OAM, assuming that participants stay on treatment and do not take rescue antihyperglycemic medication. This sample size is based on a treatment difference of 0.60% with a common standard deviation of 1.1%, using a 2-group t-test and a 0.05 two-sided significance level. The treatment differences are based on the same assumptions stated above for the treatment-regimen estimand with a 15% discontinuation rate.

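### If the MMRM falls back to an equal-variance covariance structure, the Week 40 standard error can be wrong; SAP 4.3.2 should specify empirical standard errors for that case (low priority)

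*SAP*

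**What the plan says.** SAP 4.3.2 fits change from baseline in HbA1c at each scheduled post-baseline visit by REML, with an unstructured covariance matrix and Kenward-Roger degrees of freedom. If that fails to converge, six structures are tried in a fixed order: heterogeneous Toeplitz, heterogeneous AR(1), heterogeneous compound symmetry, then Toeplitz, AR(1) and compound symmetry. The selection rule is "The first covariance structure that converges will be used". No empirical (sandwich) variance is mentioned. Protocol 9.3.1 names only the unstructured matrix and gives no fallback.

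The rule travels. For body weight, the key secondary endpoint, SAP 4.4.1.1 says that "the MMRM model (Section 4.3.2) will be updated by adding the baseline category for HbA1c", so the fallback comes with the model. SAP 4.4.2.1 builds the other repeated secondary endpoints on 4.3.2. SAP 4.6 sends the safety MMRMs to the same list, whose structures "will be tested in order until met convergence".

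The treatment-regimen estimand (SAP 4.3.1) uses an ANCOVA at Week 40 only and involves no within-participant covariance.

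**The concern.** Convergence shows that the optimiser found a solution. It does not show that the structure fits. Structures 4 to 6 estimate a single variance, roughly the average over Weeks 4 to 40, and apply it to the Week 40 contrast. Kenward-Roger adjusts for small samples under the assumed covariance; it does not repair a wrong one.

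The design makes a rising SD plausible. Protocol 6.1.1 raises tirzepatide by 2.5 mg every 4 weeks from 2.5 mg, so 15 mg is not reached before Week 20, and five of the eight visits come before any effect of the top dose. Weight change starts from zero in everyone, after a period in which weight had to be stable within 5% (Protocol 5.1). If the SD does rise, the Week 40 interval on this branch is too narrow for the primary and key secondary endpoints under the efficacy estimand, where "All tests of treatment effects will be conducted at a 2-sided alpha level of 0.05/1-sided alpha level of 0.025".

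**Working it through.** **1. The plan's own figures.** "Approximately 250 participants will be randomly assigned in a 1:1 ratio to each study arm", read as 250 in total. For a difference of 0.58% and SD 1.3% at 90% power: n = 2 × (1.960 + 1.282)² × (1.3/0.58)² = 2 × 10.51 × 5.024 ≈ 106 per arm. Allowing for 15% discontinuation, 106/0.85 = 124.7, so 125 per arm and 250 in total. For 0.60% and SD 1.1%, power is 0.977 with 106 per arm and 0.990 with 125, consistent with the stated 95% or more. The sample size reproduces. It assumes a correct standard error and says nothing about the fallback structures.

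**2. Inputs.**
- From the documents: visits at Weeks 4, 8, 12, 16, 20, 24, 32 and 40 (Protocol 1.3), so the unstructured matrix has 8 × 9/2 = 36 parameters; Week 40 HbA1c SD 1.1% (SAP 5); two-sided alpha 0.05.
- Assumed: HbA1c SD of 0.5% to 0.9% at Week 4; weight SD of 1.8 to 3.5 kg at Week 4 and 7 kg at Week 40. The documents give no SD by visit, no correlations and no weight SD.

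**3. Formula.** With complete data and a treatment-by-visit term, the Week 40 estimate is the difference in Week 40 means, so the structure affects only its standard error. For compound symmetry (and closely for the other two):

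ratio = reported SE / true SE = (root mean square SD over the 8 visits) / (Week 40 SD)

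type I error = 2 × [1 − Φ(1.96 × ratio)]

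Example: HbA1c SD rising linearly in weeks from 0.5 to 1.1 is 0.500, 0.567, 0.633, 0.700, 0.767, 0.833, 0.967, 1.100. The mean square is 0.611 and its root 0.782. The ratio is 0.782/1.1 = 0.711, and type I error is 16%.

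**4. Results for three rising shapes.** Linear; square root of time since Week 4; linear to Week 20, then flat.

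| SD, Week 4 to Week 40 | Linear | Square root | Flat from Week 20 |
|---|---|---|---|
| HbA1c 0.5 to 1.1% | 0.71; 16% | 0.79; 12% | 0.85; 9% |
| HbA1c 0.9 to 1.1% | 0.90; 8% | 0.93; 7% | 0.95; 6% |
| Weight 1.8 to 7 kg | 0.62; 22% | 0.73; 15% | 0.82; 11% |
| Weight 3.5 to 7 kg | 0.73; 15% | 0.81; 11% | 0.86; 9% |

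Each cell gives the ratio, then the type I error. In HbA1c units, the true SE with 125 per arm is 1.1 × √(2/125) = 0.139, a 95% half-width of 0.273. At a ratio of 0.854 the reported half-width would be 0.233.

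**5. Other directions, with dropout.** All three equal-variance structures were fitted by population likelihood to assumed true covariances, with 125 per arm, random dropout reaching 15% and three correlation shapes.

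| SD relative to Week 40 | Ratio | Type I error |
|---|---|---|
| Rising 0.5 to 1 | 0.74–0.77 | 13–15% |
| Rising 0.7 to 1 | 0.82–0.86 | 9–11% |
| Rising from 0.65, flat from Week 16 | 0.89–0.92 | 7–8% |
| Constant | 0.97–1.01 | 4.7–5.9% |
| Falling 1.2 to 1 | 1.06–1.12 | 2.8–3.8% |
| Falling 1.4 to 1 | 1.16–1.24 | 1.5–2.3% |

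A REML simulation (1,500 trials per cell, compound symmetry and AR(1), one correlation shape) gave 15.3% and 13.7% for the first row, 9.8% and 9.1% for the second, 7.0% and 8.8% for the third, and 4.4% and 5.3% for constant SD. The falling patterns were not simulated.

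**The case against.** The strongest reply is that the list order already does most of the work. The unstructured model comes first and all three heterogeneous structures precede any equal-variance one, so four fits must fail in turn. With about 250 participants and 36 covariance parameters that is unlikely, although its probability was not computed. The list is fixed in advance and leaves the analyst no choice. This stands, and it is why the point is minor.

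A reader might infer that reaching structures 4 to 6 necessarily makes the interval too narrow. The documents do not support that. They give one SD for this estimand, at Week 40, and the direction turns on whether Week 40 variance lies above or below the average over visits. Dose escalation shifts means, which the treatment-by-visit term already models; it does not by itself show that residual variance grows. Uninterrupted escalation also ends by Week 8 for dulaglutide and Week 20 for tirzepatide, which favours a plateau and the milder figures.

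A reader might also infer that the trial's primary conclusion as a whole is exposed. It is not: the treatment-regimen ANCOVA is untouched and SAP 2.1 handles multiplicity separately for each estimand. The additional secondary endpoints are not type I error controlled, and SAP 4.6 has a further ANCOVA fallback for safety parameters.

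Finally, a failure to converge is easier to imagine in small subgroups, but SAP 4.7.1 does not say that models are fitted within each subgroup.

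**Conclusion.** The gap is real but low in severity. On the equal-variance branch the rule can give a wrong Week 40 standard error for HbA1c and weight under the efficacy estimand, and nothing in the SAP would correct it. If the SD rises over time, the standard error is about 5% to 29% too small for HbA1c and 14% to 38% too small for weight, with type I error of about 6% to 16% and 9% to 22%. If the SD is constant the error rate stays near 5%; if it falls the test is conservative.

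These figures are conditional on four convergence failures and rest on assumed SDs; for weight both ends are assumed. They also rest on equal covariance in the two arms, no covariates, and complete data or random dropout. A rising SD is the likely pattern, more so for weight, but the documents do not establish it. The case for acting is that a prespecified fallback should be valid when it is used, since a repair after seeing the data would be post hoc.

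**What to change.** In SAP 4.3.2, state that if any structure other than unstructured is used, Week 40 inference will use empirical (sandwich) standard errors with between-within degrees of freedom in place of Kenward-Roger. Preferably also keep only heterogeneous structures 1 to 3. If the sponsor wants a last step so that the list cannot run out, structures 4 to 6 can stay provided the empirical standard error applies. Carry the rule by reference into 4.4.1.1, 4.4.2.1 and 4.6. Either a sandwich standard error or visit-specific variances returns large-sample type I error to about 5%. The calculation shows no error for structures 1 to 3; covering them is a precaution that keeps the rule simple.

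Do not fall back to an unstructured model on Weeks 24, 32 and 40 only. It removes participants who leave before Week 24. In a simulation with no true effect and assumed outcome-dependent dropout before Week 24 of 12% against 3.5%, it was biased by about 0.07% HbA1c, roughly half a standard error (0.07/0.139), while the full unstructured fit was unbiased.

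The cost is a few lines of text and a program option. Sandwich standard errors are slightly liberal in small samples. That matters little at about 125 per arm, but should be noted if the rule is used within small subgroups.
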